1.5.2 Drug Dose adjustments

1.5.2.1 Criteria for interruption of treatment with nintedanib/placebo

Treatment with nintedanib must be interrupted if any of the criteria listed in Table1 is fulfilled and in the absence of alternative probable cause.

Table 1: Criteria when to interrupt treatment with nintedanib /placebo due to an adverse event

If one criterion is met, nintedanib/placebo must be interrupted

 nausea of CTCAE grade ≥ 3 despite supportive care vomiting of CTCAE grade ≥ 2 despite supportive care diarrhea of CTCAE grade ≥ 2 for more than 3 consecutive days despite supportive care AST and/or ALT elevations of $> 2.5 \times$ ULN in conjunction with bilirubin of $> 1.5 \times$ ULN persisting after repeat testing over a 24-hour period. AST and/or ALT elevations of $> 5 \times$ ULN other non-hematological adverse event of CTCAE grade ≥ 3 considered drug-related

1.5.2.2 Criteria to restart nintedanib/placebo treatment

A patient is eligible to restart nintedanib (BIBF1120)/placebo if all criteria listed in table 2 are met. If a patient has to interrupt intake of nintedanib/placebo due to an adverse event for more than 7 days, the decision to restart treatment with nintedanib (BIBF1120) needs to be discussed and agreed upon between the investigator and the sponsor.

Table 2: Criteria to assess eligibility to restart/continue nintedanib (BIBF1120)/placebo treatment

All criteria must be met in order to restart nintedanib/placebo, meaning AEs have to return to Grade 1 or baseline, with the exceptions of the specific managements of the AE listed below

  nausea CTCAE grade \leq 2  vomiting CTCAE grade \leq 1  diarrhea CTCAE grade $<$ 2  AST and ALT $<$ 2.5 x ULN; bilirubin $<$ 1.5 x ULN  no other non-hematological adverse event grade CTCAE \geq 3 which is considered drug-related

1.5.2.3 Dose adjustments during treatment

After cycle 1, if the lifetime cumulative dose of anthracycline reaches 500mg/m², idarubicin will be switched to etoposide 100mg/m²/d day 1 to 3.

In case of severe hematologic or non-hematologic adverse events, dose of nintedanib/idarubicin/cytarabine could be adjusted for the subsequent cycles of treatment (IDA/CYTA) or when NINTEDANIB is restarted. Dose adjustment should be systematically discussed with coordinating investigator and may qualify for the definition of SAE and its related procedure. Given the toxicity profile of the different drugs it is likely that hematological toxicities will be related to idarubicin and/or cytarabine and dose adjustment will be done accordingly. Drugs are dose reduced independently and after discussion with the Protocol PI. Specific procedure should be applied in case of potential drug induced liver toxicity (see Appendices section).

Table 3

Drug	Dose level 1	Dose level -1	Dose level -2
Idarubicin (IV Push over 10-15 minutes Days 1-3	12mg/m ² /d	8mg/m ² /d	Stop drug
Cytarabine Daily (24 hr.) IV infusion Days 1-3	0.667 g/m ² /d	0.300 g/m ² /d	150mg/m ²
Nintedanib PO Days 8-28	200mg bid	150 mg bid	100 mg bid

For patients with a prior dose reduction, it could be discussed with the sponsor to re increase the dose of medication if the adverse event has fully resolved and if it was the first episode of this specific drug related AE.

Recommended dose adjustments for Nintedanib (BIBF1120)

As an initial measure for the management of side effects treatment with nintedanib should be temporarily interrupted until the specific adverse reaction has resolved to levels that allow continuation of therapy. Nintedanib treatment may be resumed at a reduced dose. Dose adjustments in 100 mg steps per day (i.e. a 50 mg reduction per dosing) based on individual safety and tolerability are recommended as described in Table 4 shown below. In case of further persistence of the adverse reaction(s), i.e. if a patient does not tolerate 100 mg twice daily, treatment with nintedanib should be discontinued.

Phase II dose reduction will be dependent on the MTD determined in Phase I. Dose reductions during phase II will be managed in 50mg increments to a minimum dose of 100mg. Patients who cannot tolerate the 100mg dose will be taken off treatment.

Table 4:

CTCAE* Adverse reaction	Dose adjustment
Diarrhea > grade 2 for more than 7 consecutive days despite anti-diarrheal treatment OR diarrhea > grade 3 despite anti-diarrheal treatment	1st episode
Vomiting ** > grade 2 AND/OR Nausea > grade 3 despite anti-emetic treatment	Reduce dose from 200 mg twice daily to 150 mg twice daily
AST and/or ALT elevations of > 2.5 x ULN in conjunction with bilirubin of > 1.5 x ULN persisting after repeat testing over a 24-hour period. OR AST and/or ALT elevations of > 5x ULN Dose adjustment/reduction will occur per dosing table 3 if Nintedanib is re-started after being held	2nd episode Reduce dose from 150 mg twice daily to 100 mg twice daily
Other non-hematological adverse reaction of > grade 3	3rd episode Stop treatment
Elevation of AST and/or ALT values to > 3 x ULN in conjunction with an increase of total bilirubin to \geq 2 x ULN and ALKP < 2 x ULN	Unless there is an alternative cause established, Nintedanib should be permanently discontinued

*CTCAE: Common Terminology Criteria for Adverse Events

Patients should PERMANENTLY discontinue treatment with nintedanib (BIBF1120) in the event of:

- Intolerable Adverse Events (CTCAE grade 3 or 4) that cannot be managed by dose reduction.
- Withdrawal of informed consent.

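### As printed, Table 4's non-liver dose-reduction rows start one grade above the hold and restart cut-offs, so six of eight grade 2–3 hold situations have no Table 4 step or counted episode

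*Combined protocol and SAP*

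**What the plan says.** Three tables in section 1.5.2 govern nintedanib/placebo after toxicity.

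- **Table 1 (1.5.2.1), hold.** The hold is compulsory: "Treatment with nintedanib must be interrupted if any of the criteria listed in Table1 is fulfilled". The non-liver criteria are nausea from grade 3, vomiting from grade 2 ("vomiting of CTCAE grade ≥ 2 despite supportive care"), diarrhea from grade 2 lasting more than 3 days, and "other non-hematological adverse event of CTCAE grade ≥ 3 considered" drug-related.
- **Table 2 (1.5.2.2), restart.** Nausea must be grade 2 or lower, vomiting grade 1 or lower and diarrhea below grade 2, with no other drug-related non-hematological event of grade 3 or higher.
- **Table 4 (1.5.2.3), recommended step and 1st/2nd/3rd episode.** The non-liver rows read "Diarrhea > grade 2 for more than 7 consecutive days despite anti-diarrheal treatment OR diarrhea > grade 3 despite anti-diarrheal treatment"; vomiting "> grade 2 AND/OR Nausea > grade 3 despite anti-emetic treatment"; and "Other non-hematological adverse reaction of > grade 3". From 200 mg bid the ladder goes to 150 mg bid; the second episode is "Reduce dose from 150 mg twice daily to 100 mg twice daily"; the third is stop.

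Below Table 4, permanent discontinuation is required for "Intolerable Adverse Events (CTCAE grade 3 or 4) that cannot be managed by dose reduction". Inside Table 4, in the liver row as extracted, a sentence says that dosing follows Table 3 when nintedanib is restarted after a hold. Table 3 lists 200, 150 and 100 mg bid and names no toxicity trigger.

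**The concern.** Tables 1 and 2 use the same grade cut-offs. Table 4, the only place that counts episodes, does not. A patient can meet a compulsory hold, recover, and return to a table that names no step for the event and does not record it as an episode.

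Two other parts of the protocol sit badly with the strict sign. The discontinuation line quoted above presumes that grade 3 events are ordinarily met first with a dose reduction. Section 1.6 makes drug-related diarrhea of grade 2 or higher lasting 8 or more days a DLT. That is the same duration as Table 4's more than 7 days, and only the grade sign differs. Most drug-related grade 3 toxicity in other organ systems is also a DLT; isolated GGT increases and hypertension controlled by optimal care are the exceptions. Grade 3 nausea and grade 2 vomiting may also qualify at 5 or more days. Such an event can thus count as dose-limiting in phase I and still trigger no Table 4 reduction for the patient who had it.

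What is at stake is consistency between sites and patients in the dose after a hold, and the frequency of dose reductions, which section 1.20.2 names as a safety output.

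**Working it through.** The plan states no figure to reproduce. The check codes the three tables as rules and lists where they disagree.

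**Step 1: lowest grade at which each rule acts.** Since > grade k means grade k+1 or higher, each printed > moves the trigger up by one grade.

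| Category | Table 1 hold from | Table 2 restart blocked from | Table 4 as printed, from | Table 4 with ≥, from |
|---|---|---|---|---|
| Nausea | 3 | 3 | 4 | 3 |
| Vomiting | 2 | 2 | 3 | 2 |
| Diarrhea | 2 | 2 | 3 | 2 |
| Other non-hematological | 3 | 3 | 4 | 3 |

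Table 2 agrees with Table 1 in 4 of 4 categories. Table 4 agrees in 0 of 4 as printed and in 4 of 4 with ≥. The liver dose-step row repeats Table 1's cut-offs, so there is no gap there.

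**Step 2: grade 2–3 non-liver holds under Table 1, with diarrhea split at 7 days.**

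| Hold situation | Table 4 step as printed | Table 4 step with ≥ |
|---|---|---|
| Nausea grade 3 | no | yes |
| Vomiting grade 2 | no | yes |
| Vomiting grade 3 | yes | yes |
| Diarrhea grade 2, 4–7 days | no | no |
| Diarrhea grade 2, 8 or more days | no | yes |
| Diarrhea grade 3, 4–7 days | no | yes |
| Diarrhea grade 3, 8 or more days | yes | yes |
| Other drug-related grade 3 | no | yes |

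As printed, 2 of 8 have a step and 8 − 2 = 6 do not. With ≥, 7 of 8 have a step, so the sign change closes 7 − 2 = 5. The sixth, grade 2 diarrhea of 4–7 days, arises from the durations (more than 3 days against more than 7), not from the sign. The total depends on how cells are split: without the 7-day split of grade 2 diarrhea, five kinds of hold lack a step as printed.

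There is also a small reverse mismatch. Grade 4 diarrhea of 1–3 days has a Table 4 step but meets no Table 1 diarrhea hold. With ≥, the same becomes true of grade 3 diarrhea of 1–3 days.

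**Step 3: effect on the episode count.** Take three successive grade 3 drug-related events in the other category, starting from 200 mg bid. As printed, Table 4 names no step at any of them. With ≥ it recommends 150 mg bid, then 100 mg bid, then stop.

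**Step 4: size of one step.** 50/200 = 25%, or 50/150 = 33%. Either is 2 × 50 = 100 mg per day. Over a full later course (days 8–28, 21 days) that is 21 × 100 = 2,100 mg. In the course of the hold itself it is less. For example, with grade 2 diarrhea on days 8–15 and restart no earlier than day 16, it is at most 13 × 100 = 1,300 mg.

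**The case against.** **The sign may be a reading artefact.** Table 4 came through the PDF reading badly: its episode column is scattered across unrelated rows, and a vomiting footnote mark has no footnote. A ≥ could have lost its bar. Against that, the sign survives in Table 4's last row, in Tables 1 and 2, and in section 1.6. Neither observation settles it, so the finding rests on the text as printed and the source file must be checked first.

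**The Table 3 sentence may supply the step.** If it was meant for every row, each restart after a hold has a dose level to go to, and only the episode count is missing. As extracted it sits in the liver row, so its reach is unclear. This is a serious limit on the point.

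**Reduction is openly discretionary.** Section 1.5.2.3 leaves a lower dose on resumption as an option, calls the Table 4 steps recommended, and has adjustments discussed with the coordinating investigator and the Protocol PI. Section 1.5.2.2 requires sponsor agreement after more than 7 days off drug. Phase II has 50 mg increments and comes off treatment if 100 mg is not tolerated. All of this stands.

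**A hold need not carry a reduction.** Table 4 does not have to equal Table 1, and the diarrhea durations show a genuine hold-only tier. The discontinuation line is also compatible with discretionary reductions. But no sentence says that the higher grades are deliberate, and the match with the DLT duration for diarrhea points the other way.

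A reader might infer that patients will be restarted at full dose after grade 3 toxicity, or that phase I safety conclusions are compromised. The documents support neither. The Table 3 sentence and the discretionary text both allow a reduction after any of these holds, and the DLT definitions in section 1.6 make no reference to Table 4.

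**Conclusion.** As printed, the mismatch is real: one grade in each of four non-liver categories, and six of eight grade 2–3 hold situations without a Table 4 step or counted episode. Five of the six turn on the sign. The wording on DLTs and on discontinuation suggests that ≥ was intended, but this is an inference.

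The practical size is uncertain. The counts are of rules, not of patients, and the documents give no event frequencies for this regimen. If the Table 3 sentence covers all holds, what is missing is the episode count. If it is confined to liver events, the step after the other holds is left to discretion.

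Severity is minor. The point affects consistency of dosing, the handling of individual patients' toxicity, and the descriptive count of dose reductions in section 1.20.2. DLT scoring, the fewer-than-2-of-6 rule, and the phase II stopping boundaries and error rates do not use Table 4 and are unaffected.

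**What to change.** 1. Check the symbol in the source file. If it is ≥, only item 3 remains.
2. If it is >, change it to ≥ in the three non-liver rows of Table 4: diarrhea from grade 2 for more than 7 days or from grade 3; vomiting from grade 2 and/or nausea from grade 3; other non-hematological reactions from grade 3. Leave the liver rows, and the hold-only tier for grade 2 diarrhea of 4–7 days, as they are.
3. State whether the Table 3 sentence applies to every hold or only to liver events.
4. If the higher grades are deliberate, say so in one sentence and give the restart dose after a hold that falls below them.

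The cost is a sign in three rows and one or two sentences in the next amendment. The downside is slightly more dose reductions and slightly lower nintedanib exposure. Grade 3 diarrhea of 1–3 days would also gain a recommended step without a Table 1 hold, and the team should confirm that it wants this. Table 4 would remain a recommendation, so discretion is narrowed, not removed.

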1.6 Definition of dose limiting toxicities (DLT) during phase I

In order to determine safety of the combination, all adverse events will be recorded on the case report forms and graded using the NCI CTC criteria (version 4.03). Toxicities not listed on the CTC will be graded as mild, moderate, or severe. The local Investigator, in consultation with the clinical staff caring for the patient, and the Protocol PI will determine the relationship to study drugs (unrelated, unlikely, possibly related, probably related, related). Dose limiting toxicity (DLT) will be either as specified below; for organ systems not included, DLT will also include any Grade III or IV non-hematologic toxicity thought possibly or probably related to study drug administration.

Specifically defined DLTs: Drug-related vomiting and nausea CTCAE grade \geq 2 for 5 or more consecutive days despite optimal supportive care. Drug-related diarrhea CTCAE grade \geq 2 persisting for 8 or more consecutive days despite optimal supportive care. Drug-related hypertension CTCAE grade \geq 3 despite optimal supportive care or intervention.

Drug-related transaminase elevation (ALT and/or AST) CTCAE grade \geq 3 or transaminase elevation CTCAE grade \geq 2 (ALT and/or AST) in conjunction with bilirubin CTCAE grade >1 . All other drug-related non-hematological toxicities of CTCAE grade \geq 3, except for isolated GGT increases. All other drug-related non-hematological toxicities of CTCAE grade 2 leading to an interruption of the BIBF 1120 treatment for \geq 14 consecutive days

Because all patients will be receiving cytarabine and idarubicin in conjunction with nintedanib, patients will not be evaluable for nintedanib- associated hematological toxicity.

Patients will have bone marrow assessed at physician's discretion by day 35 of treatment. If blood counts have not recovered, but marrow is free of morphologic evidence of leukemia, patients may be followed clinically until day 45. If counts have not recovered by day 60 and there is no morphologic evidence of leukemia, this will be considered a nintedanib- associated hematologic DLT.

If <2/6 patients experience Nintedanib attributable dose limiting toxicity, we will proceed to the randomized Phase II trial. If >/= 2 patients experience attributable DLT, six additional patients will be treated with dose level - 1 of nintedanib (150 mg BID). Assuming that <2/6 patients experience Nintedanib attributable dose limiting toxicity at the reduced dose, we will proceed to the randomized Phase II trial -1 dose level of nintedanib.

1.7 Statistical plan

The feasibility phase is structured similar to a classic 3 + 3 Phase I study. The first six patients will be treated at the targeted dose. Like most Phase I studies, this dose will be considered feasible if <2/6 patients experience attributable DLT. If at least two patients experience attributable DLT, six additional patients will be treated at dose level -1. If fewer than 2 patients experience attributable DLT, that dose will be used in the Randomized Phase II portion of the trial.

The primary endpoint of the Randomized Phase II portion is the complete remission rate. The randomized phase II portion of the study utilizes a group sequential design to test the hypothesis that arm A (nintedanib+chemotherapy) will have a complete response rate of 40% after one cycle of treatment compared to 15% in arm B (Placebo+chemotherapy). Estey, Thall, and David reviewed the outcomes of salvage therapy for AML⁴⁸. They stratified patients based on length of first remission (S1: if greater than 2 years) and whether the therapy was first or subsequent salvage (S2: first remission 1 – 2 years, S3: First remission 0- 1 year, first salvage: S4: First remission 0 – 1 year, receiving > first salvage). CR rates for S2, 3, and 4 were 47%, 14%, and 0. We will not be treating S1 in this protocol. Thus, a 40% response rate appears to be very robust for a mix of S2 to S4 patients. While it is highly unlikely that the control (placebo) arm will have a comparable CR rate, without the control arm the success of the addition of nintedanib will not be clear. Using the group sequential design we will minimize the number of patients receiving placebo. For example, if 0/8 patients in the placebo arm achieve remission, the arm will be stopped for futility. In contrast, if 5/11 patients in the nintedanib arm achieve CR, the study can be declared a success.

For Phase II, OnCore will be used to randomize the patients by assigning a sequence number that will correspond to the treatment assignment. The list that includes the sequence number with the corresponding treatment assignment will be generated by the study statistician and released only to the research pharmacist at the site. The group sequential design allows termination of either arm at early time points due to either futility or efficacy. In a randomized Phase II trial, each arm is compared to a historic control. The studies are not powered to officially compare the arms. Rather, they serve as “pick the winner” strategies. The null hypothesis is that each arm achieves a 15% response rate. The trial is powered to select an arm (presumably the experimental arm) which achieves a 40% response rate. At the point at which either arm can no longer demonstrate a 40% response rate, the arm is terminated for futility. Each arm is monitored following each accrual beginning with patient 8. The design assumes overall Type I error of 10% (1-sided) and 80% power.

The following table demonstrates the number of responses at each accrual which would stop the trial for either futility (third column) or efficacy (fourth column):

Analysis	Number of included patients	Number of responses to stop for futility	Number of responses to stop for efficacy
1	8	0	4
2	9	1	4
3	10	1	5
4	11	1	5
5	12	2	5
6	13	2	5
7	14	2	6
8	15	2	6
9	16	3	6
10	17	3	7
11	18	3	7
12	19	3	7
13	20	4	7
14	21	4	8
15	22	4	8
16	23	4	8
17	24	5	8

While this is a randomized Phase II study and each arm is ultimately statistically compared to the historical control, the response rates will be qualitatively compared between the two arms in order to get a sense whether the positive signal in the nintedanib arm is strong enough to warrant further development in larger trials.

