1.8 Patient selection

1.8.1 *Inclusion criteria*

Patient must meet all of the following criteria to be eligible for the study

1/ Patient aged 18y or older

2/ Diagnosis of AML according to WHO 2008 criteria⁴⁹. Therapy related AML may be included if in complete response and off treatment for their prior malignancy for more than 2 years. AML arising after documented MPD are excluded.

3/ Patient must meet one of the following criteria: a/ patient refractory to one or two standard induction regimen b/ patients with a first untreated relapse within 2 years of documentation of clinical remission. Patients relapsing after allogeneic stem cell transplantation are eligible if more than 6 months after transplantation and without sign of active GVHD.

4/ Patient may have been pretreated with intermediate to high dose cytarabine (more than 1000mg/m²/d over 5d) if the day of the last infusion was at least 90 days before inclusion in the study.

5/ ECOG performance status of 2 or less

6/ Patient is willing to participate to the study, has the ability to adhere to the study visit schedule and other protocol procedures, and has the ability to understand and signs an informed consent form.

7/ Women of childbearing potential must agree to use effective contraception without interruption throughout the study and for a further 3 months after the end of treatment;

8/ Men must agree to not conceive during the treatment and to use effective contraception during the treatment period (including periods of dose reduction or temporary suspension) and for a further 3 months after the end of treatment if their partner is of childbearing potential.

1.8.2 *Exclusion criteria*

Any of the following criteria excludes the patient from participating to the study.

- 1/ Patient with documented acute promyelocytic leukemia and/or PML-RAR transcript.
- 2/ Patient relapsing more than 2 years after initial remission.
- 3/ Use of any active treatment for relapse/refractory AML including but not restricted to chemotherapy, targeted agents, hypomethylating agents or investigational drugs. Use of hydroxyurea up to 6g per day for cytoreduction is allowed for a maximum of 30 days prior treatment.
- 4/ Patients with clinical evidences of active CNS disease at inclusion
- 5/ LVEF below 45% or lifetime exposure to anthracyclines over 350mg/m² of daunorubicin equivalent

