1.9 Enrollment Procedure

Prior to obtaining signed consent from a patient, the site principal investigator or coordinator must email the project manager to inquire about study space availability. If a slot is available, the potential study participant will complete the consent process. The informed consent process must be completed before any study screening procedures may begin. Following consent patients will have all required screening procedures outlined in Section 10. The site principal investigator or other approved investigator must document that the patient has met all inclusion criteria and has none of the exclusion criteria. Following completion of eligibility testing, eligibility documents will be sent to the YCCI project manager. Examples of required documents are listed in the manual of operations.

Upon review and approval by the Project Manager, the PM will send back the patients' study ID # and dose assignment (for Phase II) to the study team via email. The study team will register the patient into the Clinical Trials Management System, OnCore. During the Phase II portion of the study, the study sites will use OnCore to randomize the patient and receive a sequence # that corresponds to the study arm.

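### Phase II randomisation names no stratification factor, although the protocol cites CR rates of 47%, 14% and 0 across the patients it will enrol, so chance case mix can distort the nintedanib-versus-placebo reading

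*Combined protocol and SAP*

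**What the plan says.** Section 1.7 (Statistical plan) cites a published review of salvage therapy that grouped patients by length of first remission and line of salvage: "CR rates for S2, 3, and 4 were 47%, 14%, and 0". S2 is a first remission of 1-2 years. S3 is a first remission of up to 1 year at first salvage, and S4 is the same at a later salvage. S1 (first remission over 2 years) will not be treated. The section concludes: "Thus, a 40% response rate appears to be very robust for a mix of S2 to S4 patients". It does not state the expected shares of that mix. Section 1.8.1 leaves them open by admitting "a/ patient refractory to one or two standard induction regimen b/ patients with a first untreated relapse within 2 years of documentation of clinical remission".

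On allocation, section 1.7 says "OnCore will be used to randomize the patients by assigning a sequence number that will correspond to the treatment assignment". The study statistician generates the list, and it is released only to the site's research pharmacist. Section 1.9 adds that in Phase II "the study sites will use OnCore to randomize the patient and receive a sequence # that corresponds to the study arm". Neither section names a stratification factor, a block size or an allocation ratio, and section 1.9 describes no step at which a stratum would be entered.

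On analysis, "The null hypothesis is that each arm achieves a 15% response rate" and "The trial is powered to select an arm (presumably the experimental arm) which achieves a 40% response rate". Each arm is monitored after every patient from the 8th, and the boundary table ends at 24. The two arms are then compared qualitatively to judge whether larger trials are warranted. Section 1.7 also says that without a control arm the contribution of nintedanib would be unclear. Section 1.3.2 frames the secondary objectives (response, survival, bridging to transplant, safety) as nintedanib versus placebo.

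**The concern.** The protocol identifies a baseline factor that moves the CR rate from 47% to 0, describes nothing to balance it, and plans no analysis that adjusts for it. The arms are small. If one arm happens to receive more S2 patients, its CR rate rises with no drug effect, and the gap passes straight into the judgement for which the placebo arm exists. The comparative secondary objectives are exposed in the same way. Length of first remission and prior lines of therapy must already be established to confirm eligibility, so the factor is available before randomisation.

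**Working it through.** **1. The plan's own figures.** Section 1.7 states: "The design assumes overall Type I error of 10% (1-sided) and 80% power". Inputs: the printed futility and efficacy boundaries, with a look after every patient from 8 to 24. Method: exact binomial recursion that carries forward the probability of each response count and removes paths that cross a boundary.

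- At a true CR of 40%: P(efficacy) = 82.0%, which agrees with 80% power.
- At a true CR of 15%: P(efficacy) = 6.0%, or 9.7% if an arm still unresolved at 24 (6 or 7 responses) counts as a success. The 10% holds as a ceiling.
- Expected arm size: 11.3 patients at 15% and 11.5 at 40%. Arms will therefore usually stop near the small end of the range.

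**2. Gap between arms from case mix alone.** Let the CR rates be r = (0.47, 0.14, 0), the population shares w (assumed), and n the patients per arm under 1:1 simple randomisation (assumed). With no drug effect, the gap in expected CR is D = Σ r × (count in arm A − count in arm B) / n. Then SD(D) = √(2V/n), where V = Σwr² − (Σwr)².

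Worked case, equal thirds at n = 12:
- Σwr = (0.47 + 0.14 + 0)/3 = 0.203
- Σwr² = (0.2209 + 0.0196)/3 = 0.0802
- V = 0.0802 − 0.0413 = 0.0388
- SD(D) = √(2 × 0.0388/12) = 0.080, or 8.0 points

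The chance that |D| is 10 points or more comes from the multinomial distribution of the two arms:

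| Assumed S2/S3/S4 mix (%) | No-effect CR | 8 per arm | 12 per arm | 24 per arm |
|---|---|---|---|---|
| 10/75/15 | 15.2% | 11% | 4% | 0.4% |
| 20/50/30 | 16.4% | 25% | 14% | 4% |
| 20/40/40 | 15.0% | 27% | 16% | 4.5% |
| Equal thirds | 20.3% | 34% | 22% | 8% |

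These are two-sided, so about half of each figure favours nintedanib. Ten points is 10/25 = 40% of the 25-point effect sought (40% versus 15%).

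**3. Can case mix make the whole effect?** For equal thirds, P(|D| ≥ 25 points) is 1.1% at 8 per arm, 0.2% at 12 and about 0 at 24.

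**4. How much of the noise is case mix?** The stratum share of the variance of the observed difference is V / [p(1 − p)], where p is the no-effect CR. For equal thirds it is 0.0388/(0.203 × 0.797) = 24%. For 10/75/15 it is 0.0137/(0.152 × 0.848) = 11%.

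**5. Effect of balancing S2 against the rest.** With S2 split as evenly as possible, SD(D) at 12 per arm falls from 8.0 to 3.3 points (equal thirds) and from 6.7 to about 3.4 (20/50/30). The chance of a 10-point gap falls to about 2% or less at 8 per arm and about 0.1% or less at 12. Incomplete blocks would weaken this slightly.

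**The case against.** Four points can be made against this, and each stands in part.

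- **Silence is not a statement.** A reader might infer that the list is known to be unstratified. The documents do not say so. They neither describe nor exclude strata or blocks, so the supportable claim is that stratification is not specified.
- **The formal test is elsewhere.** A reader might infer that the trial's error rates are compromised. Each arm is tested against a fixed 15%, and section 1.7 says that the arms are not powered for a formal comparison. If patients are independent draws from a population with mean CR 15%, the binomial error rates already include chance mix. With no drug effect, fixing the mix in each arm lowers the chance that nintedanib succeeds and placebo does not only from 6.0% to 4.0% (25/25/50) or from 14.2% to 12.9% (equal thirds).
- **Ordinary sampling noise dominates.** Under equal thirds, balancing S2 reduces the SD of the observed difference only from 20 to 18 points at 8 per arm and from 16.4 to 14.7 at 12.
- **The size depends on an unstated mix.** Equal thirds implies a no-effect CR of 20.3%, which sits badly with the protocol's 15%. A large S4 share is also doubtful, because relapsed patients must be in a first untreated relapse and prior active treatment for relapsed or refractory disease is excluded. The lower rows of the range may therefore be overstated for this trial.

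What remains is the between-arm reading. The protocol itself makes that reading the purpose of the control arm, and nothing in the plan protects it from a strong, known prognostic factor.

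**Conclusion.** The point holds for the qualitative comparison of nintedanib with placebo and for the comparative secondary objectives. It does not hold to any important degree for the formal per-arm test. Assuming 1:1 allocation, simple randomisation, no dropout, the cited group CR rates and mixes from 10/75/15 to equal thirds, case mix alone shifts expected CR between arms by 10 points or more in 11-34% of trials at 8 per arm, 4-22% at 12 and 0.4-8% at 24. The risk is greatest at the arm sizes where stopping is most likely.

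A reader might go further and infer that case mix could create or wipe out the entire treatment signal. The figures do not support that: across the range used, a 25-point gap arises in about 1% of trials or fewer at 8 per arm and almost never at 12 or more. Case mix distorts the signal rather than replacing it. This is a worthwhile and inexpensive improvement, not a fatal flaw.

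**What to change.** State in sections 1.7 and 1.9 that the statistician generates the OnCore list in two strata known at screening: first remission of 1-2 years versus all others, including primary refractory patients. The sponsor should confirm that grouping, because section 1.7 does not say where refractory patients belong. State the allocation ratio. Use randomly varying block sizes that are not disclosed to sites, because non-responders are unblinded after cycle 1 (sections 1.5.1 and 1.16) and fixed blocks in small strata could make later assignments guessable. Report CR by stratum and a stratum-adjusted between-arm difference beside the overall rates.

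The cost is one extra field at randomisation, a new list, a few incomplete blocks and some residual predictability. Balance ends if one arm stops early. With so few patients, more than one factor is not advisable.

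This does not correct a trial-wide mix whose no-effect CR differs from 15%. With equal thirds that rate is 20.3%, and each arm has about a 17% chance of being declared successful with no drug effect. Reporting CR by stratum would expose this, but a remedy would need a null rate weighted to the enrolled mix or reliance on the stratum-adjusted comparison.
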